### **3.3 Effects at 3 months post treatment**

Figures 2 and 3 present trajectories of study outcomes using loess smooth curves (with 95% confidence bounds), which track changes in repeated assessment scores from baseline to 3 months post treatment. The top graph of Figure 2 fitted one trajectory to the whole sample (combined groups). It demonstrated that the average PCL-5 score declined below the lower 95% confidence limit of the baseline estimate (lower score is better) and stayed below this limit for up to 3 months post treatment.

The bottom graph (Figure 2) displays the loess curve split by group to investigate group difference in the trends. By showing overlap of their 95% confidence bounds everywhere the curves failed to reject the null hypothesis of no difference in the effects of 1 Hz versus 10 Hz rTMS treatments on PCL-5 over time. Similar patterns with equivalent interpretations for

depression symptoms (QIDS-SR) are shown in Figure 3. The loess curves for IPF and Pain score (not shown) also did not reveal a significant change in trend or treatment group difference.

- Figure 2 & 3 about here –

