Additionally, sustainability of these treatment effects was investigated using loess (local least square regression), a non-parametric approach suitable for smoothing our numerical vector, of repeated observations. Loess fits least squares regressions to localized subsets of outcome data to produce graphical description of nonlinear empirical relationships (Jacoby, 2000). The graphical displays included smooth curves plus 95% confidence bounds which allowed us to evaluate a statistically significant difference between the mean trajectory over time versus its starting baseline score. We preferred the loess method to the simple pointwise plot of estimates of the mean for two reasons: addition of pointwise 95% confidence intervals will result in less efficient use of data compared to the loess estimates that are based on regressions in local neighborhood of each time point; and an alternative use of standard error of the mean around each estimate is not appropriate for inference as it underestimates the variability between individuals within the study sample (Diong et al., 2018; Nagele, 2003).

The proportions of side effects and dropouts per group were captured. Given the low proportions, a nonparametric binomial test was used to test for significant group difference in their proportions. Two-sided p-values were calculated and used to assess statistical significance defined as  $p < 0.05$ . All statistical analysis was carried out using the R statistical application.

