### **3.2 Effects at the end of 30 treatments**

The results of the two-sample t-tests failed to reject the null hypothesis of no significant difference between the two treatment groups (Table 2) in improvement on the CAPS ( $p = 0.77$ ) and IPF ( $p = 0.69$ ) scores from baseline to post-30.

- Table 2 about here –

The secondary analyses, however, yielded some significant findings with respect to the primary outcomes (Table 2). For the 1 Hz group, a paired t-test indicated that PTSD symptoms as measured by CAPS scores were significantly lower by the 30th treatment (improved,  $p = .03$ ). The scores on MADRS, PCL-5, and QIDS-SR also significantly improved. The change in function as measured by the IPF, however, did not quite reach significance ( $p=0.075$ ) in the 1 Hz group. In contrast, the 10 Hz group demonstrated significant improvement from baseline to the 30th treatment on all outcomes listed except pain score. (Table 2) Similarly, there was failure to reject the null hypothesis of no relationship between the groups on either response or remission rate by 30th treatment (Table 3).

- Table 3 about here –

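### The 3-month durability reading rests on a loess plot rule that is not a 5% test; paired 1- and 3-month contrasts on data already collected should carry it

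*Combined protocol and SAP*

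**What the plan says.** Section 2.3 (Data Analysis) declares two-sided p-values with a 0.05 threshold. It presents the loess curves with 95% bounds as a means to "evaluate a statistically significant difference between the mean trajectory over time versus its starting baseline score". The t-tests in that section define improvement from baseline to the 30th treatment and go no further.

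Section 3.3 applies two reading rules to the plots.

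- **Durability.** The upper graph of Figure 2 "fitted one trajectory to the whole sample (combined groups"). The text continues: "It demonstrated that the average PCL-5 score declined below the lower 95% confidence limit of the baseline estimate", and says the curve "stayed below this limit for up to 3 months post treatment". QIDS-SR is given the same interpretation.
- **Groups.** For the PCL-5 curves split by arm, the conclusion reads: "By showing overlap of their 95% confidence bounds everywhere the curves failed to reject the null hypothesis of no difference".

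It adds: "The loess curves for IPF and Pain score (not shown) also did not reveal a significant change in trend or treatment group difference".

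The text gives no estimate, interval or p-value for change to 1 or 3 months. It does not state the loess span, degree, standard-error method or handling of repeated measures. Nor does it say whether the combined curve used 35, 27 or 26 people. Figures 2 and 3 and their captions are not visible here.

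**The concern.** A confidence limit around the baseline mean describes the uncertainty of that mean alone. Asking whether a later mean falls below it treats the later mean as known without error, and ignores that the same people supply both values. The first omission makes the rule too lenient. The second makes it too strict when within-person correlation is high. The net error rate depends on quantities the text does not report.

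What is at stake is the positive statement that PCL-5 and QIDS-SR gains held to 3 months. The paired tests in section 3.2 support improvement at the 30th treatment only, so persistence beyond that point rests on the plot rule. The primary Welch tests on CAPS and IPF are unaffected.

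**Working it through.** **Inputs from the documents.** Two-sided 0.05 (section 2.3). Randomized: 17 + 18 = 35. Completing follow-up: 14 in the 1 Hz arm and 13 - 1 = 12 in the 10 Hz arm, so 26 in all and 35 - 26 = 9 not contributing (section 3.1). PCL-5, QIDS-SR, pain and IPF were collected at 1 and 3 months; CAPS, MADRS and NSI were not collected after the 30th treatment (section 2.2.3). The documents state no error rate for either plot rule, so there is no figure to reproduce.

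**Assumed.** Within-person correlation rho, SD ratio and all loess settings.

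**1. Durability rule, simple means, one visit.** With no true change and equal SDs, the chance that the follow-up mean falls below the baseline lower limit is P(Z > 1.96 / sqrt(n0/n1 + 1 - 2 rho)), where n0 and n1 are the numbers at baseline and follow-up. The nominal one-direction value is 2.5%.

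| rho | n0 = n1 = 26 | n0 = 35, n1 = 26 |
|---|---|---|
| 0 | 8.3% | 10.0% |
| 0.3 | 4.9% | 6.9% |
| 0.5 | 2.5% | 4.6% |
| 0.7 | 0.6% | 2.2% |

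Example: rho = 0.3 with 26 and 26 gives sqrt(1 + 1 - 0.6) = 1.183, 1.96/1.183 = 1.657, and a tail of 4.9%.

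The rule equals nominal when the square-root term is 1. With equal SDs and the same people that is rho = 0.5. With 35 and 26 it is rho = 35/(2 x 26) = 0.67. With the same people and an SD ratio k (follow-up to baseline), the term is sqrt(1 + k^2 - 2 k rho), which is 1 when k = 2 rho. At k = 1.2 and rho = 0.5 it is sqrt(1.24), and the error is 3.9%. Agreement with 2.5% therefore occurs only for particular combinations.

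**2. Durability rule, loess version.** This is a simulation under no change: 26 people, visits at weeks 0 to 6, 9, 13 and 22, tricube weights, and standard errors that treat every row as independent. Degree/span was 2/0.75, 1/0.75 or 2/0.5. Correlation was exchangeable or decaying with time, from 0 to 0.9.

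- Curve below the baseline limit at 3 months: about 0% to 16-18%.
- Curve below it at week 6 and at every later visit to 3 months: 0% to about 4%.
- In the same settings, the paired t-test from baseline to 3 months rejected in 4.3% to 6.2% of trials (two-sided), and the Welch test on change in 4.2% to 5.8%. Both agree with 5% within simulation error.

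**3. Overlap rule, one visit, independent groups.** With correct, equal SEs the size is 2 P(Z > 1.96 x 2/sqrt(2)) = 2 P(Z > 2.77) = 0.56%, not 5%. For 14 and 12 people (normal approximation), its power is 7% against 25% for a direct test at a true difference of 0.5 SD, and 23% against 53% at 0.8 SD.

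**4. Precision of direct contrasts.** 95% CI half-width in SDs of change: combined, t(25)/sqrt(26) = 0.40; between arms, t(24) x sqrt(1/14 + 1/12) = 0.81; within arm, t(13)/sqrt(14) = 0.58 and t(11)/sqrt(12) = 0.64.

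**The case against.** **The null readings are already hedged.** Section 3.5 says that nothing definitive follows from a failure to reject. That covers the overlap statement and the IPF and pain sentence. It stands, and it is why the overlap rule is secondary here. It does not reach the positive durability reading.

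**The durability sentence describes a curve and gives no p-value.** True, but section 2.3 tells the reader that the bounds serve to judge significance against baseline, so the sentence will be read that way.

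**Section 2.3 prefers loess for efficiency.** Borrowing from neighbouring visits is a fair reason to draw the curve. It does not turn a comparison with one limit into a test of change.

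**The figures may state what the text omits.** Captions could give the sample and settings. That would narrow the error range, but the rule would still not be a contrast.

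Two stronger readings are tempting and are not supported.

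- *That the 3-month benefit is spurious.* The text says the curve stayed below the limit. Under no decline at all, that stricter pattern was rare in the simulations (0% to about 4%), so the reading may be conservative.
- *That the IPF results expose a contradiction.* Section 3.2 says of the 1 Hz arm "The change in function as measured by the IPF, however, did not quite reach significance" (p = 0.075), and reports improvement in the 10 Hz arm by the 30th "treatment on all outcomes listed except pain score". Those two results alone allow a combined paired p as high as 0.032. Adding the between-arm p = 0.69 brings it below 0.01 (0.0043 with equal SDs of change). Section 3.3 nevertheless reports no significant IPF trend. But section 3.2 ends at the 30th treatment and the curve runs to 3 months. A gain that later faded would fit both, and the IPF curve is not shown.

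**Conclusion.** The concern holds for the durability reading and for the significance wording attached to the loess plots. Neither rule is a 5% test. For simple means, the baseline-limit rule has a one-direction error from 0.6% to 10.0% over the correlations and samples tabulated, against a nominal 2.5%. For the loess version at 3 months it runs from about 0% to 16-18%. The text does not let a reader place the trial within these ranges, or even tell the direction of the departure. The loess figures rest on assumed visit weeks, correlation, span, degree and independent-row standard errors; the closed-form figures rest on assumed correlation, SD ratio and sample.

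The persistence of PCL-5 and QIDS-SR improvement is unquantified in the text rather than refuted. The statement should be corrected, but it does not touch the primary comparison.

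**What to change.** For PCL-5 and QIDS-SR, report with 95% CIs:

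1. the change from baseline to 1 month and to 3 months by paired t-test, combined and per arm;
2. the 1 Hz versus 10 Hz difference in that change by Welch t-test.

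Give IPF and pain as supportive. Name the combined 3-month PCL-5 change as the main durability contrast. Label all of these post hoc and unadjusted for multiplicity, and state that 26 of the 35 randomized (14 and 12) contribute. Keep the loess curves as descriptive plots. Remove the significance and failed-to-reject wording attached to them in sections 2.3 and 3.3, including the IPF and pain sentence.

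The work is a reanalysis of collected data with tests section 2.3 already names, plus wording. Its costs are these.

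- The contrasts are post hoc, and the main one is chosen after the curve was seen.
- The full set is 4 outcomes x 2 times x 4 contrasts = 32, with 32 x 0.05 = 1.6 false positives expected if every null is true. Hence one named contrast, with the rest as estimates.
- Precision is limited: about 0.40 SD of change combined and 0.81 SD between arms.
- Nine of 35 randomized are omitted.
- The durability statement may become less favourable.
- With no sham arm and entry on PCL-5 of at least 45, a valid paired test still does not separate lasting benefit from regression to the mean. CAPS has no follow-up data, so durability on that outcome cannot be tested.

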### **3.4 Tolerability of treatment**

With respect to patient safety, there were no significant events related to the treatment in this trial. There were two Serious Adverse Events (SAE) that were unrelated to the study interventions. There were no seizures and no continuing complications. The 10 Hz group had two participants (2/18 or 11%) that could not tolerate the treatment at the first visit but no such report from the 1 Hz participants (see Figure 1). Exact binomial tests (2-sided) failed to show significant differences between the two randomized groups on the proportions of Veterans who reported headache, site pain during treatment, or stopped treatment due to side effects (Table 4).

- Table 4 about here –

### **3.5 Post-hoc power calculations**

Given that the final group sample sizes of 14 and 13 (see Figure 1) used to test our primary hypothesis fell short of our anticipated evaluable sample of 40, inadequate statistical power was suspected. Therefore, post-hoc power calculations were performed based on the statistics obtained from the results of t-tests for CAPS-5 (Table 2). Using a paired samples t-test with alpha of 0.05, there were 98% and 76% power (for 10 Hz and 1 Hz groups respectively) to reject the null hypothesis of no difference between the baseline and post-30 scores (that the mean of the paired differences is zero); which support the conclusions reached from our significant results. For the nonsignificant results of 1 Hz versus 10 Hz, however, there was low power to

reject the null hypothesis of no difference in group means using a two-sided two-sample unequal-variance t-test with alpha of 0.05. Therefore, no definitive conclusion can be derived from any failure to reject the null (i.e. non-significant findings) in this study. Although we did not find a definitive conclusion with our study, the preliminary results are that if a difference exists at the group level, it is not likely a large clinical difference.

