### **3. RESULTS**

#### **3.1 Patient population**

Participant recruitment, enrollment, assignment to study conditions, and study retention are presented as a Consort diagram in Figure 1. Forty-four participants were enrolled with data

being acquired from September 2014 until February 2018. Nine veterans were not randomized with six failing to meet diagnostic criteria by CAPS-5, one was determined to have a history of seizures, one was unable to get off work, and one was unable to have motor threshold determined. Of the 35 randomized, 17 were allocated to the 1 Hz group and 18 to the 10 Hz group. Of the 17 veterans in the 1 Hz group, 14 completed the primary endpoint and all subsequent visits. The three participants who did not reach the primary endpoint included two that stopped due to work concerns and one who was lost to follow-up. Of the 18 veterans in the 10 Hz group, 13 completed the primary endpoints with one of those not completing the taper or follow-up visits. The five who did not reach the primary endpoint included two that could not tolerate the first treatment, one stopped due to headaches from another medical condition, one was too frustrated by parking, and one was lost to follow-up. A total of 27 who completed the primary end points constituted the final sample for testing the primary hypothesis, and they had no missing data on the tested outcomes.

- Figure 1 about here –

There were no significant differences between treatment groups on their baseline assessment scores, including demographic and baseline rating scales. (Table 1)

- Table 1 about here –

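### Section 3.5 reports 76% post-hoc power without stating sidedness (about 62% under the trial's two-sided rule), treats it as support for the p-value it restates, and closes on a size claim with no interval or threshold in the text

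*Combined protocol and SAP*

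**What the plan says.** Section 2.3 (Data Analysis) makes p-values two-sided with significance at p < 0.05, and specifies a paired t-test for change within each group and a Welch test between groups.

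Section 3.1 gives the 1 Hz numbers: "Of the 17 veterans in the 1 Hz group, 14 completed the primary endpoint and all subsequent visits". Thirteen reached the primary endpoint in the 10 Hz group, and the 27 analysed had complete data on the tested outcomes.

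Section 3.2 reports that for 1 Hz "a paired t-test indicated that PTSD symptoms as measured by CAPS scores were significantly lower by the" 30th treatment, with p = .03. Between groups, the tests "failed to reject the null hypothesis of no significant difference between the two treatment groups", with p = 0.77 for CAPS and p = 0.69 for IPF.

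Section 3.5 bases post-hoc power on the observed CAPS-5 t-test results and makes three statements:

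- On the paired tests: "Using a paired samples t-test with alpha of 0.05, there were 98% and 76% power" (10 Hz and 1 Hz respectively), "which support the conclusions reached from our significant results".
- On the comparison of groups, power was low "using a two-sided two-sample unequal-variance t-test with alpha of 0.05", so that "no definitive conclusion can be derived from any failure to reject the null".
- As a preliminary reading to close: "if a difference exists at the group level, it is not likely a large clinical difference".

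**The concern.** There are three linked problems.

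- **Sidedness.** The paired-power sentence omits it, although the sentence on between-group power says two-sided and Section 2.3 sets a two-sided rule. A reader will take 76% as two-sided, and it looks too high for p = .03 with 14 pairs.
- **Use of the figure.** Power evaluated at the observed effect is presented as backing for the significant result. It is computed from that same result and brings no new evidence.
- **Closing inference.** After stating that nothing definitive follows from non-significance, the section offers a view on the size of the difference. The text supplies neither an interval nor a meaning for large, and this is the section's last word on the primary 1 Hz versus 10 Hz question.

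At stake are an overstated power figure, presented as corroboration, and a conclusion on the primary comparison that readers cannot weigh from the text.

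**Working it through.** **Inputs.** n = 14 and 13 (Sections 3.1 and 3.5); paired test and two-sided 0.05 rule (Section 2.3); 1 Hz paired CAPS p = .03, between-group p = 0.77 (CAPS) and 0.69 (IPF) (Section 3.2); stated power 76% and 98% (Section 3.5). Table 2 is not shown in the text available for review, so means, SDs and exact p-values could not be used.

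**1. Reproducing the 76%.** With df = 13, two-sided p = .03 gives t = 2.436 and a standardised paired effect dz = t/√n = 2.436/√14 = 0.651. Observed power uses noncentrality dz × √n = 2.436:

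- two-sided power = P(|T| > t(0.975; 13)), with T noncentral t on 13 df
- one-sided power = P(T > t(0.95; 13))

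| Two-sided p (all round to .03) | Two-sided power | One-sided power |
|---|---|---|
| .025 | 64.9% | 77.4% |
| .030 | 61.6% | 74.6% |
| .035 | 58.6% | 72.0% |

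A simulation of 400,000 runs at p = .03 gave 61.7% and 74.6%. The two-sided normal approximation gives 68.3% (65.3% to 71.7%), still short of 76%.

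Working backwards, a stated 76% (75.5% to 76.5%) requires:

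- two-sided: t = 2.867 to 2.902, p = .0132 to .0124, which does not round to .03
- one-sided: t = 2.467 to 2.501, two-sided p = .0283 to .0266, which does

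So with n = 14 the figure is reproduced one-sided and not two-sided. The gap is 76 − 61.6 = 14.4 points.

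**2. The 98% for 10 Hz.** No 10 Hz CAPS p-value is in the text, so this cannot be checked. If it was one-sided, t = 3.933 on 12 df and the two-sided value would be about 95% (94% to 96% for a stated figure of 97.5% to 98.5%).

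**3. Does observed power add support?** For fixed n and alpha, p determines t, and t is the noncentrality. Power is therefore a one-to-one function of p. At exactly p = .05 with n = 14 (t = 2.160), two-sided observed power is 51.6%. Any larger value says only that p was below .05.

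**4. What the between-group p-values imply.** Assume equal SDs, so df = 25. The standard-error factor is √(1/14 + 1/13) = 0.385, d = t × 0.385, and the 95% interval is (t ± 2.060) × 0.385. Positive means the direction of the observed difference, because the p-values do not show which group did better.

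| Outcome | p | t | d | 95% CI (SD) | 90% CI (SD) |
|---|---|---|---|---|---|
| CAPS | 0.77 | 0.296 | 0.11 | −0.68 to 0.91 | −0.54 to 0.77 |
| IPF | 0.69 | 0.404 | 0.16 | −0.64 to 0.95 | −0.50 to 0.81 |

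Taking 0.8 SD as large (a yardstick chosen here; the document sets none), the share of the confidence distribution beyond it in either direction is 0.0435 + 0.0128 = 5.6% for CAPS and 0.0533 + 0.0101 = 6.3% for IPF. Two-sided power for a true 0.8 SD with 14 versus 13 is 51%.

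Sensitivity: noncentral-t 95% intervals are −0.64 to 0.87 (CAPS) and −0.60 to 0.91 (IPF). With Welch df as low as 12 and the same standard-error factor, they are −0.72 to 0.95 and −0.68 to 1.00. All pass 0.8 SD on the upper side.

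**The case against.** The strongest reply concerns the closing sentence. It is hedged twice, as preliminary and as only not likely, and it does not claim that a large difference is excluded. About 94% of the confidence distribution lies within 0.8 SD for both outcomes, and the 90% interval for CAPS lies wholly inside, so the numbers lean the sentence's way. The 0.8 SD yardstick is not the document's, the intervals pass it narrowly, and under equal SDs a 1.0 SD threshold would not be crossed. Table 2 may already hold an interval. This stands: the sentence is not shown to be false. What it lacks, in the text, is the interval and threshold that would let a reader judge it.

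On the 76%, the cause is not settled. At the printed p = .03, one-sided power is 74.6%, and an exact match needs an unrounded p of about .027 to .028. Applying the same effect size to the 17 randomised with a two-sided normal approximation gives 0.651 × √17 − 1.96 = 0.72, or about 76.6%. But Section 3.5 names groups of 14 and 13, so that route conflicts with its own text. One-sidedness remains the better explanation, not a proven one.

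Finally, consequences are limited. The paired tests are supplementary, and neither p = .03 nor the null between-group result changes. That is a fair reason not to rate the point higher, but it does not make the 76% correct or the support clause valid.

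**Conclusion.** The concern holds as a should-fix point.

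- **The 76%** cannot be two-sided power for n = 14 and a p that rounds to .03; the two-sided value is about 62% (58.6% to 64.9%). This rests on the printed p and n and on the section's statement that observed statistics were used. One-sided calculation is inferred, and the 98% is uncheckable.
- **The support clause** is invalid whatever the sidedness, and this needs no unseen table.
- **The closing inference** has no stated basis in the text. Under equal SDs and a 0.8 SD yardstick, the data make a large difference look improbable but do not exclude it in one direction.

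The reported p-values, the failure to reject, and the statements of low between-group power and no definitive conclusion stand.

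**What to change.** 1. Delete the clause saying the power figures support the significant results.
2. Drop the 76%, or state its sidedness and give the two-sided value (about 62% from the printed p; the exact value from the unrounded result). Check the 98% in the same way.
3. Report in the text the between-group differences in CAPS and IPF change with Welch 95% confidence intervals in scale points.
4. Replace the closing sentence with wording such as: the 95% CI for the difference in CAPS change was [a] to [b] points; it [does / does not] exclude a difference of [threshold] points. Do the same for IPF. Name the source of each threshold and label it post hoc, since the text defines none.

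The rest of the paragraph (shortfall from 40 evaluable, low between-group power, no definitive conclusion) can stay.

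The cost is text only. The intervals come from t-tests already run, with no new data or analysis. The 1 Hz power figure becomes less favourable, and the closing statement is limited to what the interval excludes.
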